6.2 IMPORTANT PROTOCOL DEVIATIONS

Data discrepancies and deviations from the CTP will be identified for all treated subjects.

Section 7.3 of the CTP: *Important protocol deviations (iPD) categories will be suggested in the integrated quality and risk management (IQRM) plan, iPDs will be identified no later than in the Report Planning Meeting, and the iPD categories will be updated as needed.*

Consistency check listings (for identification of deviations of time windows) and a list of protocol deviations (e.g. deviations in drug administration, in blood sampling times, etc.) will be provided to be discussed at the Report Planning Meeting and database lock meeting (RPM/DBLM). At this meeting, all manual deviations identified at the sites by the CRAs and deviations too complex to program will be reviewed by the trial team to decide which are considered important. For definition of important protocol deviations (iPD), and for the process of identification of these, refer to the Boehringer Ingelheim (BI) SOP "Identify and Manage Important Protocol Deviations (iPD)" ([2](#)).

If any iPDs are identified, they are to be summarised into categories and will be captured in the RPM/DBLM minutes via an accompanying Excel spreadsheet ([3](#)).

The iPDs will be summarised and listed.

6.3 SUBJECT SETS ANALYSED

- **Treated set (TS):**

This subject set includes all subjects who were entered and treated with at least one dose of study drug.

This is the full analysis set population in the sense of ICH-E9 ([1](#)).

The TS is used for safety analyses.

Section 7.3.1 of the CTP: *Plasma concentration data and parameters of a subject will be included in the statistical pharmacokinetic (PK) analyses if they are not flagged for exclusion due to a protocol deviation relevant to the evaluation of PK (to be decided no later than in the Report Planning Meeting) or due to PK non-evaluability (as revealed during data analysis, based on the criteria specified below). Exclusion of a subject's data will be documented in the CTR.*

Relevant protocol deviations may be

- *Incorrect trial medication taken, i.e. the subject received at least one dose of trial medication the subject was not assigned to*
- *Incorrect dose of trial medication taken*
- *Use of restricted medications*

Plasma concentrations and/or parameters of a subject will be considered as non-evaluable, if for example

- *The subject experienced emesis that occurred at or before two times median t_{max} of the respective treatment (Median t_{max} is to be determined excluding the subjects experiencing emesis),*
- *A predose concentration of BI 730357 is >5% C_{max} value of that subject in the respective treatment period*
- *Missing samples/concentration data at important phases of PK disposition curve*
- **PK parameter analysis set (PKS):**
This subject set includes all subjects in the TS who provide at least one PK endpoint that was defined as primary or secondary and was not excluded due to a protocol deviation relevant to the evaluation of PK or due to PK non-evaluability. Thus, a subject will be included in the PKS, even if he contributes only one PK parameter value for one period to the statistical assessment. Descriptive and model based analyses of PK parameters will be based on the PKS.

The descriptive analysis of PK concentrations will be based on the ADS ADPC as described at the beginning of [Section 7](#).

Table 6.3: 1 Subject sets analysed

Class of endpoint	Subject set	
	TS	PKS
Analyses of PK endpoints		X
Safety endpoints	X	
Demographic/baseline endpoints	X	
Important PDs	X	
Disposition	X	

6.5 POOLING OF CENTRES

This section is not applicable, because the study was performed in only one centre.

6.6 HANDLING OF MISSING DATA AND OUTLIERS

Handling of missing data and outliers will be performed as described in the CTP, Section 7.5.

The only exceptions where imputation might be necessary for safety evaluation are AE dates. Missing or incomplete AE dates are imputed according to BI standards (see 001-MCG-156_RD-01 ([4](#))).

Missing data and outliers of PK data are handled according to BI standards (see 001-MCS-36-472_RD-01) ([5](#)).

6.7 BASELINE, TIME WINDOWS AND CALCULATED VISITS

The baseline value is defined as the last measurement before administration of BI 730357 in each period.

Section 6.1 of the CTP: *Exact times of measurements outside the permitted time windows will be documented. The acceptable time windows for screening and the end of trial examination are provided in the CTP Flow Chart.*

Study measurements and assessments scheduled to occur 'before' trial medication administration are to be performed and completed within a 3h-period prior to BI 730357 administration in Visit 2, and within a 2h-period prior to the next itraconazole administration in Visit 3, if not indicated otherwise in the Flow Chart.

Following administration of trial drugs in Visits 2 and 3, the acceptable deviation from the scheduled time for vital signs, ECG, and laboratory tests will be ± 30 min on Day 1, ± 45 min on Day 2, and ± 60 min from Day 3 onwards.

[...]

For planned blood sampling times, refer to the Flow Chart. While these nominal times should be adhered to as closely as possible, the actual sampling times will be recorded and used for the determination of pharmacokinetic parameters.

Starting from 119 hours after BI 730357 administration (and beyond), a time window of ± 60 min will be allowed for PK blood sampling times.

If a subject misses an appointment, it will be rescheduled if possible. The relevance of measurements outside the permitted time windows will be assessed no later than at the Report Planning Meeting.

Adherence to time windows will be checked via the consistency check listings at the RPM/DBLM.

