mode of admin.	Oral with 240 mL of water after an overnight fast of at least 10 h

Proprietary confidential information © 2019 Boehringer Ingelheim International GmbH or one or more of its affiliated companies

Test product 2	Itraconazole oral solution (Sempera® Liquid 10 mg/mL)
dose	200 mg once daily for 12 days in treatment T
mode of admin.	Oral with 240 mL of water after an overnight fast of at least 9 h
Duration of treatment	
Treatment R (BI 730357 alone): Single dose of 50 mg BI 730357 (Day 1)
 
Treatment T (itraconazole + BI 730357): 12 days of itraconazole treatment (200 mg itraconazole once daily) combined with a single dose of 50 mg BI 730357 (Day 1) on the fourth day of the itraconazole treatment (1 h after the itraconazole administration)
 
Wash-out period Administrations of BI 730357 will be separated by a wash-out phase of at least 10 days

Statistical methods	Relative bioavailability will be estimated by the ratios of the geometric means (test/reference) for the primary and secondary endpoints. Additionally, their two-sided 90% confidence intervals (CIs) will be provided. This method corresponds to the two one-sided t-tests procedure, each at a 5% significance level. Since the main focus is on estimation and not testing, a formal hypothesis test and associated acceptance range is not specified. The statistical model will be an analysis of variance (ANOVA) on the logarithmic scale including effects for 'subjects' and 'treatment'. CIs will be calculated based on the residual error from the ANOVA. Descriptive statistics will be calculated for all endpoints.

Proprietary confidential information © 2019 Boehringer Ingelheim International GmbH or one or more of its affiliated companies

FLOW CHART

Period	Visit	Day	Planned time (relative to BI 73 0357 administration) [h:min]	Approximate clock time of actual day [h:min]	Event and comment	Safety laboratory ⁹	PK _{blood} (BI 730357)	12-lead ECG	Vital signs (BP, PR)	Questioning for AEs and concomitant therapy ⁶
SCR	1	-21 to -1			Screening (SCR) ¹	A				
Period 1 / Treatment R (BI 730357 alone) ⁷			2	-3 to -1	-75:00 ⁸	06:00	Ambulatory visit	B ⁸		
			1	-3:00	06:00	Admission to trial site	x ^{3,5}	x ³		
			0:00	09:00	BI 730357 administration					
			0:30	09:30		x				
			1:00	10:00		x				
			1:30	10:30		x				
			2:00	11:00	240 mL fluid intake	x				
			2:30	11:30		x				
			3:00	12:00		x				
			3:30	12:30		x				
			4:00	13:00	240 mL fluid intake, thereafter lunch ¹⁰	x				

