2.2.2.2 Safety and tolerability

Safety and tolerability of BI 730357 and itraconazole will be assessed based on:

- Adverse events (including clinically relevant findings from the physical examination)
- Safety laboratory tests
- 12-lead ECG
- Vital signs (blood pressure, pulse rate)

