4.1.4 Drug assignment and administration of doses for each subject

This trial is a one-way crossover study. All subjects will receive the 2 treatments in fixed order. The treatments to be evaluated are outlined in Table [4.1.4: 1](#) below.

Table 4.1.4: 1 Dosage and treatment schedule

Treatment period	Treatment	Substance	Formulation	Unit strength	Dosage	Total dose
1	R (Reference)	BI 730357	Tablet	50 mg	1 tablet on Day 1	50 mg
2	T (Test)	BI 730357 Itraconazole	Tablet Oral solution	50 mg 10 mg/mL	1 tablet on Day 1 20 mL (200 mg) on Days -3 to Day 9	50 mg 2400 mg

Administration of trial medication will be performed after subjects have fasted overnight; fasting is to start no later than 10 h before the scheduled dosing of BI 730357 and no later than 9 h before dosing of itraconazole.

The investigator (or authorised designee) will administer the trial medication as an oral dose together with about 240 mL of water to subjects who are in a standing position. For drug administration, the so-called four-eye principle (two-person rule) should be applied. For this, one authorised employee of the trial site should witness the administration of trial medication, and – if applicable – its preparation (e.g. reconstitution), if correct dosage cannot be ensured otherwise.

For restrictions with regard to diet, see Section [4.2.2.2](#).

Subjects will be kept under close medical surveillance until 24 h after drug administration of BI 730357. During the first 4 h after drug administration of BI 730357, subjects are not allowed to lie down (i.e. no declination of the upper body of more than 45 degrees from upright posture), except for medical reasons or for recording of 12-lead ECG and vital signs measurements.

The treatments will be separated by a wash-out phase of at least 10 days between administrations of BI 730357.

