7.3.4 Safety analyses

Safety will be analysed based on the assessments described in Section [2.2.2.2](#). All treated subjects (TS, refer to Section [7.3](#)) will be included in the safety analysis. Safety analyses will be descriptive in nature and based on BI standards. No hypothesis testing is planned.

For all analyses, the treatment actually administered (= treatment at onset) to the subject will be used (any deviations from the randomised treatment will be discussed in the minutes of the Report Planning Meeting).

Treatments will be compared in a descriptive way. Tabulations of frequencies/proportions will be used to evaluate categorical (qualitative) data, and tabulations of descriptive statistics will be used to analyse continuous (quantitative) data.

Measurements (such as ECG, vital signs, or laboratory parameters) or AEs will be assigned to treatments (see Section [4.1](#)) based on the actual treatment at the planned time of the measurement or on the recorded time of AE onset (concept of treatment emergent AEs). Therefore, measurements planned or AEs recorded prior to first intake of trial medication will be assigned to the screening period, those between first trial medication intake and end of REP (see Section [1.2.3](#)) will be assigned to the treatment period. Events occurring after the REP but prior to next intake or end of trial termination date will be assigned to 'follow-up'. In case of two or more treatments, the follow-up will be summarized according to the previous treatment. These assignments including the corresponding time intervals will be defined in detail in the TSAP. Note that AEs occurring after the last per protocol contact but entered before final database lock will be reported to Pharmacovigilance only and will not be captured in the trial database.

Additionally, further treatment intervals (analysing treatments) may be defined in the TSAP in order to provide summary statistics for time intervals, such as combined treatments, on-treatment totals, or periods without treatment effects (such as screening and follow-up intervals).

Adverse events will be coded using the Medical Dictionary for Regulatory Activities (MedDRA). Frequency, severity, and causal relationship of AEs will be tabulated by treatment, system organ class, and preferred term. SAEs, AESIs (see Section [5.2.6.1](#)), and other significant AEs (according to ICH E3) will be listed separately.

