- a total over all on treatment phases involving BI (“**Total on treatment BI**“)
- a total over all on treatment phases included in this analysis (“**Total on treatment**“)

B) Section 15.4 and Appendix 16.1.13.1.8 (except for ClinicalTrials.gov and EudraCT) of the CTR displays:

- Screening
- On treatment (labelled with the name of the study treatment (short label))
- Follow-up BI (labelled “**FU BI**“)
- Follow-up BI+ITZ (labelled “**FU BI+ITZ**“)

In Section 16.1.13.1.8 AE tables, the following totals will be provided in addition:

- a total over all on treatment phases involving BI (“**Total BI**“)
- a total over all study phases (“**Total**“)

Tables of vital signs and laboratory values will present results by study period including baseline of the respective period.

For detailed information on the handling of the treatments in the O*C views refer to Technical TSAP ADS plan and Analysis Data Reviewers guide.

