7.8.3 Vital signs

Descriptive statistics over time including change from baseline will be performed for vital signs (blood pressure and pulse rate). In the listing the difference from baseline will also be displayed.

Clinically relevant findings in vital signs will be reported as AEs.

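### The Period 2 vital-sign baseline follows three itraconazole doses and precedes the fourth, so change from baseline under T shows neither the full effect of T nor the added effect of BI 730357 alone

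*SAP*

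**What the plan says.** SAP 6.7 fixes the reference value for both periods: "The baseline value is defined as the last measurement before administration of BI 730357 in each period". SAP 7.8.3 applies it: "Descriptive statistics over time including change from baseline will be performed for vital signs (blood pressure and pulse rate"). SAP 6.1 adds: "Tables of vital signs and laboratory values will present results by study period including baseline of the respective period".

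The protocol synopsis describes treatment T as "12 days of itraconazole treatment (200 mg itraconazole once daily) combined with a single dose of 50 mg BI 730357", with BI 730357 given "on the fourth day of the itraconazole treatment (1 h after the itraconazole administration"). The dosing table in protocol 4.1.4 gives the itraconazole schedule as "20 mL (200 mg) on Days -3 to Day 9".

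The safety objective in protocol 2.2.2.2 names both drugs: "Safety and tolerability of BI 730357 and itraconazole will be assessed based on". Protocol 7.3.4 says: "Treatments will be compared in a descriptive way". For adverse events only, SAP 6.1 separates an itraconazole-alone phase from the BI + ITZ phase. For vital signs the SAP defines no such phase and no pre-itraconazole baseline.

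**The concern.** Treatment T begins with the first itraconazole dose on Day -3, but its vital-sign baseline is taken on Day 1. The Period 1 baseline is free of trial drug; the Period 2 baseline is not. A blood-pressure or pulse shift produced by the first three itraconazole doses is part of the T baseline, so it is subtracted from every T change score.

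The planned baseline does not isolate BI 730357 either. The Day 1 pre-dose procedures are completed before itraconazole dose 4, which is given one hour before BI 730357. The T change score is therefore BI 730357 plus part of the itraconazole effect, whereas the R change score is BI 730357 alone.

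At stake is the reading of a descriptive safety table. A shift under T could look smaller than it was. If the end-of-trial value is compared with the same baseline, a return to normal could look like a fall.

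**Working it through.** **Step 1: count the doses around the baseline.** The protocol Flow Chart places itraconazole at -73, -49, -25, -1, 23, 47, 71, 95, 119, 143, 167 and 191 h relative to BI 730357. That is 12 doses; 12 × 200 mg = 2400 mg, the total in protocol 4.1.4. Flow Chart footnote 2 puts the Period 2 Day 1 pre-dose procedures within 2 h before the itraconazole dose at -1:00.

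- Doses before the baseline: 3 of 12.
- Doses after the baseline: 9 of 12.

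| Vital signs at | Doses since planned baseline | Doses since a pre-itraconazole baseline |
|---|---|---|
| 1:30 | 1 | 4 |
| 4:00 | 1 | 4 |
| 24:00 | 2 | 5 |

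The Flow Chart columns are damaged in the text available, so these times are the apparent vital-sign times. It is also unclear whether the marks on Days -3 to -1 mean vital signs or adverse-event questioning. The last value before BI 730357 is on Day 1 either way.

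**Step 2: size of the part removed.** Inputs: half-life about 40 h (protocol 1.2.2) and a 24 h dosing interval. Assumptions: linear accumulation, immediate absorption, and an effect proportional to the amount present. Protocol 1.2.2 says the kinetics are non-linear, so the result is only indicative.

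- Fraction left after one interval: r = 0.5^(24/40) = 0.660.
- Amount at baseline, in dose units: r + r² + r³ = 1.382.
- Steady-state trough: r / (1 - r) = 1.939.
- Share already in the baseline: 1.382 / 1.939 = 0.713, or 71%.

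As a check on this share, protocol 1.2.2 gives mean peaks of 547.7 ng/mL after one dose and 1965 ng/mL after 15 days. Assuming exponential build-up between them, the share after three doses is 1 - (1 - 547.7/1965)³ = 0.62. A range of roughly 62% to 71% is reasonable.

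**Step 3: what the change score would show.** Take an illustrative itraconazole effect of +5 bpm at steady-state trough and no effect of BI 730357. The effect at a given time is 5 × amount / 1.939.

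- At 1:30, which is 2.5 h after dose 4: amount = (1.382 + 1) × 0.5^(2.5/40) = 2.281.
- At 24:00, which is 1 h after dose 5: amount = (2.382 × 0.660 + 1) × 0.5^(1/40) = 2.527.
- At end of trial, Days 18 to 25, 217 to 385 h after the last dose: amount = (1 - r¹²)/(1 - r) × 0.5^(217/40) = 0.068, falling to 0.004.

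| Time | Against a drug-free value | Against the planned baseline |
|---|---|---|
| 1:30 | 5 × 2.281/1.939 = +5.9 bpm | 5 × (2.281 - 1.382)/1.939 = +2.3 bpm |
| 24:00 | 5 × 2.527/1.939 = +6.5 bpm | 5 × (2.527 - 1.382)/1.939 = +3.0 bpm |
| End of trial | +0.2 to 0.0 bpm | -3.4 to -3.6 bpm, about -3.5 |

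The gap between the columns is constant: 5 × 0.713 = 3.6 bpm. It scales with the assumed effect: about 1.4 bpm for a 2 bpm trough effect and about 7.1 bpm for 10 bpm.

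**The case against.** The best defence is that the same anchor, the last value before BI 730357, is used in both periods. The trial asks how itraconazole alters the exposure to BI 730357, so change after BI 730357, alone or on an itraconazole background, is a legitimate contrast. It also matches the adverse-event phases in SAP 6.1, where BI + ITZ starts at the BI 730357 dose. This stands as a reason to keep the planned baseline. It does not make the T change score a clean measure of BI 730357, because itraconazole dose 4 falls between the baseline and BI 730357.

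Much is visible already. Tables show each period's baseline, individual values are listed, and clinically relevant vital-sign findings become adverse events with their own itraconazole-alone phase. This stands, and it limits the consequence.

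A reader might infer more than the documents support:

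- **That the T change score omits the itraconazole effect.** It does not. Dose 4 precedes every post-dose vital sign, and dose 5 precedes the one at 24 h. Only what doses 1 to 3 had produced is removed.
- **That T and R are not comparable.** They are comparable as change after BI 730357. They are not comparable as the effect of each full treatment against a drug-free start.
- **That the laboratory analysis is affected.** The last scheduled Period 2 safety laboratory before BI 730357 appears to be on Day -3, before itraconazole, so the same rule gives a different kind of baseline there. SAP 7.8.2 compares laboratory values with reference ranges and plans no change from baseline, so nothing follows from this.

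**Conclusion.** The point holds as a minor gap in a descriptive safety analysis and a cheap improvement, not as the correction of an invalid analysis. That three of the twelve itraconazole doses precede the T vital-sign baseline follows directly from the documents. So does the absence of any planned change score from an itraconazole-free value, although the safety objective covers both drugs.

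The size is indicative only. The 71% rests on the stated half-life and on linear accumulation, which the protocol's own description of the kinetics contradicts. The bpm figures also rest on rapid absorption, a proportional effect and an invented 5 bpm; the documents report no itraconazole effect on pulse or blood pressure. The end-of-trial reversal applies only if that visit is compared with the Period 2 baseline, which the SAP does not settle. The PK endpoints and the adverse-event phases are unaffected.

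**What to change.** - Keep the planned baseline. State in SAP 6.7 and 7.8.3 that in Period 2 it reflects change after BI 730357 on an itraconazole background, with further itraconazole doses given after it.
- Add, for Period 2 and end of trial, a supplementary change from the last itraconazole-free value. Use the Day -3 pre-dose vital signs if they are measured, otherwise the Period 1 Day 1 pre-dose value.
- Use the supplementary change when describing the effect of the full treatment T against R.
- State which baseline applies to the end-of-trial value.

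The cost is a few lines of SAP text and one extra column in the vital-sign tables and listing. No new measurement is needed. If the Period 1 value has to serve, it lies at least 10 days before Period 2 Day 1, so the supplementary change carries some between-period variation; a footnote should say so.

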7. PLANNED ANALYSIS

Safety analysis (refer to [Section 7.8](#)) will be performed by and will be presented in Sections 15.1 to 15.4 of the CTR and in Appendix 16.2 and 16.1.13.1.

Inferential statistical analyses of PK endpoints (refer to Sections [7.4](#) and [7.5.2](#)) will also be performed by and will be presented in Section 15.5 of the CTR and in Appendix 16.1.13.3.

Descriptive data analysis of PK endpoints will be performed by and will be presented in Section 15.6 of the CTR.

The format of the listings and tables will follow the standards defined in the BI corporate guideline “Reporting of Clinical Trials and Project Summaries” [001-MCG-159] ([6](#)) with the exception of those generated for PK-calculations ([8](#)).

The individual values of all subjects will be listed, sorted by treatment sequence, subject number, visit and actual treatment (if appropriate).

The listings will be included in Appendix 16.2 of the CTR.

For end-of-text tables, the set of summary statistics for non-PK parameters is:

N	number non-missing observations
Mean	arithmetic mean
SD	standard deviation
Min	minimum
Median	median
Max	maximum

For analyte concentrations, the following descriptive statistics will additionally be calculated:

CV	arithmetic coefficient of variation
gMean	geometric mean
gCV	geometric coefficient of variation

The data format for descriptive statistics of concentrations will be identical with the data format of the respective concentrations. The descriptive statistics of PK parameters will be calculated using the individual values with the number of decimal places as provided by the evaluation program. Then the individual values as well as the descriptive statistics will be reported with three significant digits in the CTR.

Tabulations of frequencies for categorical data will include all possible categories and will display the number of observations in a category, as well as the percentage (%) for each treatment group. Percentages will be rounded to one decimal place and will be based on all

subjects in the respective subject set whether they have non-missing values or not. The category 'missing' will be displayed only if there are actually missing values.

Units of variables should be given in the titles or column/row descriptors in square brackets (e.g. [mg]).

Exclusion of PK parameters

The ADS ADPP (PK parameters) contains column variables indicating inclusion/exclusion (APEXC) of a PK parameter and an analysis flag comment (APEXCO). All analyses based on the PKS will include parameters if they are not flagged for exclusion, that is APEXCO is equal to "Included".

Exclusion of PK concentrations

The ADS ADPC (PK concentrations per time-point or per time-interval) contains column variables ACEXC or ACEXCO indicating inclusion/exclusion (ACEXC) of a concentration and an analysis flag comment (ACEXCO). Exclusion of a concentration depends on the analysis flag comment ACEXCO. For example, if ACEXCO is set to 'ALL CALC', the value will be excluded for all types of analyses based on concentrations. If ACEXCO is set to 'DESC STATS', the value will be excluded from descriptive evaluations per planned time point/time interval. If ACEXCO contains the addition 'TIME VIOLATION' or 'TIME DEVIATION', the value can be used for further analyses based on actual times. If ACEXCO is set to 'HALF LIFE', the value will be excluded from half-life calculation (and, as a consequence, any calculation that relies on λ_z) only; the value is included for all other analyses.

Further details are given in 001-MCS-36-472_RD-01 "Noncompartmental Pharmacokinetic / Pharmacodynamic Analyses of Clinical Studies" ([5](#)) and 001-MCS-36-472_RD-03 "Description of Analytical Transfer Files and PK/PD Data Files" ([7](#)).

